One method to attack these deficiencies in current program practice is to attack the time component of the hemostasis equation. In doing so, it is hypothesized that if radial artery compression time can be shortened to 40 minutes or less, the following could result: improved catheterization lab efficiency, greater patient satisfaction and lower complication rates, including RAO, may be improved. As concerns improved cath lab efficiency, a system that standardizes compression technique and shortens compression time to that which is fully under the supervision and care of cath lab holding room personnel, will also eliminate the variability of recovery staff needing to manage the hemostasis band / site, and complications typically associated with patient management being carried out in multiple settings within the hospital. To summarize, the potential advantages of a hemostasis system for PCI incorporating the benefits of the StatSeal technology used in combination with a hemostasis band as compared to a hemostasis band alone may include:

- Decreased radial artery compression times, aka Band In Place (BIP) time.
- Decreased incidence of RAO complications at discharge, or 24 hours, whichever occurs first
- Decreased incidence of other complications associated with TRA, such as hematoma, bleeding, and oozing.
- Elimination or reduction in the need for additional equipment, such as Doppler units, plethysmographs and pulse oximeters to assess hemostasis band efficacy
- Facilitate arterial site management to the more specialized catheterization lab staff/personnel that are better trained to recognize complications that occur during (BIP) band in place time.
- Decreasing the workload to the staff by virtue of shortened band in place times and improve procedural throughput.
- Facilitate greater patient comfort resulting from decrease band in place time and faster wound healing.

To do so, the effects of anticoagulation used during a PCI must be taken in to account.

II. DESCRIPTION OF THE STUDY DEVICE:

Recently, a new compound – potassium ferrate, in combination with a hydrophylic polymer which is formed in to a disc when compressed - has been used in conjunction with hemostasis bands to shorten compression times. This product (trade name StatSeal Advanced) is an FDA

approved product comprised of a topical hydrophilic polymer and potassium ferrate disc, [Photo 1] formed by compression of the compound.

Photo 1: StatSeal Advanced Disc

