The sample size of 120 patients is estimated to have 90% power to detect an average difference in time to removal of the TR band of 60 minutes between the SSA and TRB groups, using a relatively large standard deviation of 100 minutes and a two-sided alpha of 0.05.

Descriptive summary statistics will be presented for all study variables. Continuous variables will be displayed as means with standard deviations and medians with 75th and 25th percentiles. Categorical variables will be summarized as frequencies with their respective percentages with two-sided 95% exact confidence intervals of the percentages. Statistical comparisons for continuous variables will be performed using the Student's t test or Mann-Whitney U test, as appropriate. Comparisons for categorical variables will be performed using the Chi square test or Fisher exact test, as appropriate. A two-sided P value of 0.05 will be considered statistically significant.

Categorical variables will include, but are not limited to:

- Percent of patients in each arm with total TTH of 60 minutes or less.
- Percent of patients in each arm with TTH of 40 minutes or less without complication.
- The percentage of patients in each arm with bleeding, oozing or hematoma during TTH, further delineated by the EASY bleeding and hematoma classification attached.
- Percent of patients in each arm with RAO at each /all follow-up points.
- Percent of patients in each arm with radial patency as tested with Pleth-ox at each designated test time point.

Primary Efficacy Outcomes:

In each arm the:

- Total Time to Hemostasis (TTH), defined as the total time the HMS applies compressive force until successful hemostasis is achieved without complication.

Secondary Efficacy Outcomes:

In each arm the:

- Percent of patients free from radial artery occlusion at discharge or at 24 hours, whichever occurs first.
- Percent of patients with Barbeau test patterns A,B,C,D at initial application of the HMS
- Percent of SSA patients with Barbeau test patterns A,B,C,D after 20' of HMS time.
- Percent of patients with Barbeau test patterns A,B,C,D at full deflation of the HMS. (40' for SSA group; per protocol in the TRB group)
- Percent of patients with Barbeau test patterns A,B,C,D at discharge or at 24 hours, whichever occurs first.
- Percent of patients in whom successful hemostasis is achieved in one hour or less.

Primary Safety Outcome:

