A PROSPECTIVE RANDOMIZED STUDY COMPARING THE INCIDENCE OF RADIAL ARTERY OCCLUSION (RAO) AND THE TIME TO HEMOSTASIS (TTH) WHEN USING A HEMOSTASIS BAND ALONE AND IN CONJUNCTION WITH A DISC COMPRISED OF POTASSIUM FERRATE (STATSEAL ADVANCED) FOLLOWING TRANSRADIAL CATHETERIZATION. Study Sponsor: A Physician Initiated Study

Principal Investigator: [name], MPA

Cardiology Division Veterans Medical Center Long Beach

Statistical Analysis

Continuous data are presented as mean \pm standard deviation and as median [interquartile range], and compared using unpaired t-test and Mann-Whitney U-test, respectively. Discrete data are presented as frequencies with their respective percentages and compared using Fisher's exact test. Outcome data were analyzed on an intention-to-treat basis. Two-tailed tests of significance are reported and p values < 0.05 were considered statistically significant. Univariate logistic regression was performed using all baseline patient and procedural variables available to predict the secondary outcome of hematoma formation. Variables that were significant in univariate analysis at $p<0.25$ were retained and entered into a multivariate model with a threshold of $p<0.05$ being considered as significant. Statistical analyses were performed using the SPSS statistical software program (SPSS version 16.0.2, Chicago, IL).

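### The between-arm secondary, categorical and safety comparisons are all judged at two-sided p<0.05 with no testing order or exploratory label, so isolated chance differences can be reported as findings

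*SAP*

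**What the plan says.** The SAP (Statistical Analysis) states: "Two-tailed tests of significance are reported and p values < 0.05 were considered statistically significant". Protocol section VI agrees: "A two-sided P value of 0.05 will be considered statistically significant". Neither text limits the rule to particular outcomes.

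The outcomes under the rule are:

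- **Categorical variables (section VI):** five bullets, introduced by "Categorical variables will include, but are not limited to". Some cover several time points, for example "Percent of patients in each arm with radial patency as tested with Pleth-ox at each designated test time point".
- **Secondary efficacy (section VI):** six bullets. One concerns SSA patients only, so five are between-arm.
- **Safety (section VI):** one primary and two secondary outcomes.

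Section VI names TTH as the single primary efficacy outcome and puts freedom from RAO among the secondary ones. Section III lists both RAO and TTH as primary objectives. The sample size covers time only: "The sample size of 120 patients is estimated to have 90% power" for a "difference in time to removal of the TR band of 60 minutes between the SSA and TRB groups". The potential advantages listed under The Clinical Need include less RAO and "Decreased incidence of other complications associated with TRA, such as hematoma, bleeding, and oozing".

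**The concern.** The labels primary and secondary rank the outcomes by name. They do not say which results may be called statistically significant, or in what order. The RAO, Barbeau and bleeding comparisons matter here because the TTH difference is largely set by the compression schedules: the control band stays inflated for 2 hours, while the SSA band is fully deflated at 40 minutes. The clinical message is therefore likely to come from outcomes that the trial was not sized for. If SSA changes none of them, the chance that at least one crosses 0.05 can exceed 5%. The plan as written would let that result be reported as a benefit, or as a harm, on the same footing as the primary result.

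**Working it through.** **1. The plan's own figure.** Inputs from section VI: a 60-minute difference, "using a relatively large standard deviation of 100 minutes and a two-sided alpha of 0.05", 60 per arm. The standardised shift is 60 / (100 × √(2/60)) = 3.29. Normal approximation: Φ(3.29 − 1.96) = 0.908. Noncentral t: 0.903. The stated 90% is reproduced, and the alpha statements agree with each other. This figure covers the time outcome only.

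**2. Benchmark at nominal size.** For k independent null tests, the chance of at least one p<0.05 is 1 − 0.95^k: 22.6% for k = 5 and 33.7% for k = 8. In favour of SSA only, 1 − 0.975^5 = 11.9%.

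**3. True size of Fisher's test, which the SAP specifies.** By exact enumeration with equal event rates in both arms:

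| Event rate | 60/arm, either direction | 60/arm, favouring SSA | 90/arm, either direction | 90/arm, favouring SSA |
|---|---|---|---|---|
| 2% | 0.0008 | 0.0004 | 0.0034 | 0.0017 |
| 5% | 0.0105 | 0.0053 | 0.0187 | 0.0093 |
| 10% | 0.0218 | 0.0109 | 0.0305 | 0.0152 |
| 20% | 0.0282 | 0.0141 | 0.0325 | 0.0162 |
| 30% | 0.0308 | 0.0154 | 0.0344 | 0.0172 |

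**4. Five binary access-site outcomes.** These are RAO at full deflation, RAO at discharge or 24 hours, bleeding/oozing/hematoma, primary safety, and minor access-site events. The protocol gives a background rate only for RAO (5-10%). The other rates are assumptions.

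- *Lower set (5, 5, 20, 2, 10%), 60 per arm:* 1 − 0.9895² × 0.9718 × 0.9992 × 0.9782 = 7.0% in either direction; 1 − 0.9947² × 0.9859 × 0.9996 × 0.9891 = 3.6% favouring SSA.
- *Lower set, 90 per arm:* 1 − 0.9813² × 0.9675 × 0.9966 × 0.9695 = 10.0%; 1 − 0.9907² × 0.9838 × 0.9983 × 0.9848 = 5.1% favouring SSA.
- *Higher set (10, 10, 30, 10, 30%), 60 per arm:* 1 − 0.9782³ × 0.9692² = 12.1%; 1 − 0.9891³ × 0.9846² = 6.2% favouring SSA.
- *Higher set, 90 per arm:* 1 − 0.9695³ × 0.9656² = 15.0%; 1 − 0.9848³ × 0.9828² = 7.7% favouring SSA.

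A within-patient latent correlation of 0.5 lowers these only slightly.

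**5. Eight tests.** Add the four-category Barbeau pattern at full deflation and at discharge, and complications away from the access site. A simulation used no arm effect, Barbeau D at 5-10%, other events at 2-35%, latent correlation 0 or 0.5, and 1,500 trials per scenario. With Fisher-type exact tests, at least one p<0.05 in either direction occurred in 13.5-20.8% of trials at 60 per arm and 16.7-23.4% at 90.

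**6. Uncorrected chi-square, which section VI also allows.** Eight tests: 25-33%. Five tests at 60 per arm: lower set, 1 − 0.9541² × 0.9501 × 0.9807 × 0.9495 = 19.5%; higher set, 1 − 0.9495³ × 0.9475² = 23.2%.

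**7. Left out.** The 40- and 60-minute TTH cut-offs cannot be null, because the control band is inflated for 2 hours. Exams made under the band are left out for the same kind of reason.

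**The case against.** - **Direction.** A reader might infer that 14-23% is the chance of a spurious vascular or bleeding advantage for SSA. The calculation does not support this. That range counts either direction over eight tests. Two of them are four-category comparisons with no direction, and one concerns complications away from the access site. For the five binary access-site outcomes, the chance favouring SSA is about 3-6% at 60 per arm and 5-8% at 90. Fisher's conservatism absorbs much of the multiplicity.
- **Choice of label.** A reader might infer that the discharge exam can be reported under whichever name reaches 0.05. This mostly fails. RAO, freedom from RAO and patency at that exam form one 2×2 table and give one p-value. Only the A-D pattern is a different test.
- **Not all are clean nulls.** The full-deflation exams follow different compression schedules, and bleeding during TTH is counted over a much longer window in the control arm. Setting aside the two such outcomes among the five leaves three. The either-direction chance is then 1 − 0.9895 × 0.9992 × 0.9782 = 3.3% (lower set, 60 per arm) to 1 − 0.9695² × 0.9656 = 9.2% (higher set, 90 per arm). The two set aside remain hard to interpret, because the schedules alone could separate the arms.
- **Partly handled, and common practice.** Section VI names one primary efficacy outcome, promises descriptive summaries of all variables and plans exact 95% intervals for percentages. Unadjusted secondary outcomes are usual in a study of this size. This stands as a limit on severity. It does not supply the missing statement of what may be claimed.

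**Conclusion.** The point holds. One 0.05 rule covers an open-ended, overlapping list of between-arm comparisons, with no testing order and no exploratory label. With no arm effect and Fisher's exact test, the chance of at least one p<0.05 in either direction is about 7-12% at 60 per arm and 10-15% at 90 over five binary access-site outcomes, about half of it favouring SSA. It is about 14-23% over eight tests, and higher with uncorrected chi-square. These figures rest on assumed event rates of 2-35% and on the choice of which tests form the family, neither of which the documents fix.

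Two broader readings go too far. The plan does have a hierarchy of names; what it lacks is a testing hierarchy. And the TTH conclusion is not put in doubt: its test stays at two-sided 0.05 with the stated power.

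**What to change.** First reconcile section III, which lists RAO and TTH both as primary objectives, with section VI, which makes only TTH primary. Then, in section VI and the SAP:

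1. Limit the term statistically significant to TTH at two-sided 0.05 and then, only if TTH is significant, freedom from RAO at discharge or 24 hours at 0.05.
2. Label all other efficacy and categorical comparisons exploratory, reported as between-arm differences with 95% confidence intervals and no significance claim.
3. Report the discharge exam once as RAO and once as Barbeau pattern, and drop the duplicate lines.
4. Report the safety outcomes as unadjusted between-arm differences with 95% confidence intervals, so that no harm signal is suppressed.

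The cost is wording in two documents. It needs no patients or data, and the TTH test loses no power. The downside is that an isolated p<0.05 on an exploratory outcome can no longer be presented as an established benefit.

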2. A subject withdraws consent to participate. Patients who withdraw from the study will be replaced and excluded from data analysis.

[figure not shown]
Protocol:

Control patients: Patients will have a TR band applied over the arteriotomy site and inflated with 15-18ml of air. After aspirating and clearing the contents of the sheath, the radial sheath will be removed. The TR band will be deflated until bleeding occurs, and 2 ml of air will be reintroduced to provide hemostasis. Patent hemostasis will be documented with plethysmography and oximetry as described below within 5 minutes after band application and removal, and within 30 min of discharge or after 24 hours. The TR band will be left inflated and in place for 2 hours following the procedure for all patients (regardless of diagnostic or PCI procedure), after which deflation attempts will commence.

Statseal Protocol: Patients will have a Statseal Advance (SSA) disc applied after withdrawing the radial sheath 2-4 cm. A Tegaderm dressing will be applied to secure the disc position. The TR band will be applied over the SSA disc with the center of the balloon (the green dot) over the center of the SSA disc. The TR band will be inflated with 8cc of air (which is typically occlusive pressure), and the sheath removed. No deflation will occur immediately. After 20 minutes of pressure, 3 cc of air will be removed from the TR band. After an additional 20 minutes (40 minutes after procedure), the TR band will be completely deflated, and the TR band left in place. After an additional 20 minutes (60 minutes after procedure) the TR band will be removed.

[rest of page intentionally blank]

STUDY OVERVIEW GRAPHIC

V. STUDY ACTIVITIES & GUIDELINES

Inspection Prior to Use

Prior to initiating any study activities, inspect the HMS devices for any damage. Do not use any device that appears compromised or damaged.

Required Accessories for each experiment

- Hemostasis Band (TR Band, Terumo, Inc.)
- StatSeal Advanced disc (if randomized to test group)
- Pulse oximeter

ACTIVITIES AND ASSESSMENTS

Informed Consent:

Subjects must have read the contents of the written informed consent document, had all questions regarding the study adequately answered by study staff, and signed and dated the document prior to any study related activities. See Appendix 1 for a sample of the Informed Consent document.

Definitions of Baseline and Procedural Variables:

Smoking: Active smoking or >20 pack year tobacco history.

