Diabetes: Hgb A1C >6.5% or active medical treatment for diabetes.

Hypercholesterolemia: LDL >130 or on treatment with antilipemic agents.

Hypertension: >140/80 or on medical treatment for hypertension.

Diagnostic procedure: Involving diagnostic catheters only.

Interventional procedure: Involving an interventional wire and therapeutic ACT typically >200, including for fractional flow reserve measurement where a stent is not placed.

Single wall puncture: Use of micropuncture wire and anterior wall puncture only.

Double wall puncture: Use of double wall puncture and sheath withdrawal technique.

Number of forward attempts: Number of forward advancements of the needle required to obtain access (not number of separate punctures of skin).

Procedure Start Time: Time when lidocaine is administered, prior to first puncture attempt.

Procedure End Time: Time when sheath is removed.

Test methodology:

All Pleth-ox testing will be done by qualified personnel with results classified according to Barbeau test pattern classifications. [Barbeau, et al. *Evaluation of ulnopalmar arterial arches with pulse oximetry and plethysmography; comparison with the Allen's test in 1010 patients. Am Heart Journal; 2004; 147:489-493*]

At the start of the TRA procedure, prior to radial artery cannulation, a baseline Pleth-ox exam will be performed for all patients and recorded on the CRF. Ulnar compression will be applied to confirm that the radial artery is patent. Patients with a type D pattern exam will be excluded from the study.

At the conclusion of a successful transradial procedure, the patient will be randomized to either SSA or TRB, each device applied per protocol & IFU.

Following placement of the HMS system, Pleth-Ox exams will be performed at the following time points with results recorded in the CRFs.

- Within 5 minutes of initial HMS placement
- In the SSA (StatSeal Advanced) group, within 5 minutes of the first partial deflation (20 minutes after initial placement).
- Within 5 minutes of full deflation of the HMS in both groups
- Within 30' of discharge or 24 hours post procedure (\pm 1 hour), whichever occurs first.

VI. STUDY STATISTICAL PLAN:

This is a physician initiated, prospective, randomized, two-arm study, to be conducted at up to four experienced 'Radial First' centers with the principal investigator having a (minimum) ten case experience using StatSeal Advanced.

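### The SAP's only multivariable model, for hematoma, picks its terms by univariate p<0.25 and does not force in the randomized arm, so the adjusted model can omit the hemostasis method.

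*SAP*

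**What the plan says.** The SAP's single paragraph describes one multivariable analysis: "Univariate logistic regression was performed using all baseline patient and procedural variables available to predict the secondary outcome of hematoma formation". Variables with univariate p below 0.25 "were retained and entered into a multivariate model with a threshold of" p<0.05 for significance.

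The paragraph does not say:
- whether the randomized arm is a candidate or is kept in the model;
- whether the p values are Wald, score or likelihood ratio (it says only "Statistical analyses were performed using the SPSS statistical software program", version 16.0.2);
- how a factor level with no events is handled;
- which hematoma grades are modelled. Protocol section VI puts classes III to V under primary safety and classes I and II under secondary safety.

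Separately, discrete data are "compared using Fisher's exact test", and "Outcome data were analyzed on an intention-to-treat basis". Protocol section VI lists among the categorical variables: "The percentage of patients in each arm with bleeding, oozing or hematoma during TTH". Hematoma is therefore compared between arms outside the model.

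Protocol section V, under "Definitions of Baseline and Procedural Variables", includes: "Procedure End Time: Time when sheath is removed".

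**The concern.** The trial compares two ways of achieving hemostasis, and hematoma is one of the complications they might change. A model of hematoma that omits the method can present independent predictors without adjusting for the factor the trial randomized. The SAP wording allows this on either reading. If the arm is not a baseline or procedural variable, it never enters. If it counts as procedural, it enters only by passing p<0.25.

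A second weakness depends on the software output used. When one level of a binary factor has no events (quasi-complete separation), the maximum-likelihood log odds ratio is infinite and the Wald p value goes to about 1. A Wald screen then drops the term however strong the association.

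A minor third point is that the wording admits any procedural variable, including procedure duration. Under the protocol's definition, duration ends at sheath removal. That comes after the envelope is opened and after arm-specific application steps.

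**Working it through.** **The plan's own figure.** The only sized outcome is time to band removal: difference 60 min, SD 100 min, two-sided alpha 0.05, power 90% (Protocol section VI). Per arm, n = 2 × (1.960 + 1.282)² × 100² / 60² = 58.4, so 59 per arm and 118 in total. The t-distribution version gives 59.4, so 60 per arm and 120 in total, with power 0.903. The stated 120 reproduces. No figure is given for the hematoma model.

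**Inputs.** There are 60 patients per arm (Protocol section IV) and the screen is at p<0.25 (SAP). The hematoma rates are my assumptions, because neither document gives one.

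**How often the arm fails the screen.** I enumerated every pair of event counts (a, c) at 60 per arm, weighted each by its binomial probability, and summed the weights of pairs with p≥0.25. The Wald statistic is the log odds ratio divided by √(1/a + 1/(60−a) + 1/c + 1/(60−c)), with p set to 1 if either count is zero. The likelihood-ratio (LR) statistic is twice the log-likelihood gain, on 1 df. The chance that at least one arm has no events is (1−p₁)⁶⁰ + (1−p₂)⁶⁰ minus their product.

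| Assumed rates | Arm dropped, Wald | Arm dropped, LR | An arm has zero events |
|---|---|---|---|
| 10% v 2% | 52% | 19% | 30% (0.98⁶⁰ = 0.298) |
| 10% v 5% | 59% | 50% | 4.8% (0.95⁶⁰ = 0.046) |
| 20% v 5% | 12% | 7% | 4.6% |
| 20% v 10% | 34% | 34% | 0.2% (0.90⁶⁰ = 0.002) |

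At 90 per arm (the maximum of 180), 20% v 10% still loses the arm in 22% of trials. At 10% v 5%, LR alone accounts for 50 of the 59 points, so low power is the main cause. Only at 10% v 2% does separation dominate: it supplies 30 of the 33 points between 52% and 19%.

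**The separation mechanism, 6/60 v 0/60.**
- Wald: after 20 iterations the log odds ratio is 19.0 with SE 5189, so z = 0.0037 and p = 0.997.
- LR: the log-likelihood with the arm is 6 ln 0.10 + 54 ln 0.90 = −19.505. Without it, 6 ln 0.05 + 114 ln 0.95 = −23.822. The statistic is 2 × 4.317 = 8.63, p = 0.003.
- Fisher's exact test: p = 0.027.
- Firth: odds ratio (6.5 × 60.5)/(54.5 × 0.5) = 14.4, penalized LR p = 0.011.
- With one event in the sparse arm (6 v 1), Wald p = 0.086 and the arm is kept. The failure needs a true zero.

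**Events per candidate.** The protocol defines at least 8 baseline and procedural variables by my count, taking start and end times as one. For overall rates of 2% to 30%, expected events are 2.4 to 36 at N=120 and 3.6 to 54 at N=180. That is 0.3 to 4.5 and 0.45 to 6.75 events per variable. With 8 independent null candidates, p<0.25 admits 8 × 0.25 = 2 on average, and at least one with probability 1 − 0.75⁸ = 90%.

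**Timing.** The protocol randomizes at the conclusion of a successful procedure. In the StatSeal arm, the sheath is partly withdrawn, the disc and dressing are placed and the band is inflated before the sheath is removed. In the control arm, the band is applied and inflated first. Duration to sheath removal is therefore measured after assignment.

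**The case against.** The strongest objection is that the randomized comparison does not depend on this model. A reader might infer that a real device effect could be reported as no relation to hematoma. The documents do not support that: the by-arm comparison uses Fisher's exact test, which gives p = 0.027 in the 6 v 0 example. This objection stands, and it limits the point to the adjusted model.

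A reader might also infer that hematomas will be few and that the screen will discard the strongest effects. Neither is established. No rate is given, and the count depends on grades the SAP does not specify. The p≈1 failure needs both a Wald screen, which the SAP does not specify, and a zero-event level. For the arm that is uncommon except at 10% v 2%. Unrelated factors can also have a zero-event level by chance, but dropping an unrelated factor is the right outcome and shows no harm.

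It can be argued that a risk-factor model need not estimate a treatment effect. That is a fair difference of purpose. Even so, patient predictors in a randomized device trial are easier to interpret with the device in the model, and the SAP should say which was intended.

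On duration, the SAP never names it as a candidate, and only application steps separate assignment from sheath removal. No size can be given, so the point stays minor.

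**Conclusion.** The point holds in limited form. The SAP sets a data-driven entry rule for its only multivariable model and does not keep the randomized arm, so the adjusted hematoma model can omit the hemostasis method. At 60 per arm, the chance that the arm fails the screen is 59% (Wald) or 50% (LR) at 10% v 5%, and 34% by either at 20% v 10%. All of these rest on assumed rates and on the arm being a candidate at all. If it is not a candidate, it is always absent.

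Loss through separation is conditional on Wald p values and a zero-event arm: 30% of trials at 10% v 2%, under 5% at 10% v 5% or 20% v 5%, and 0.2% at 20% v 10%. The unadjusted test of hematoma by arm remains valid. Because the model concerns a secondary outcome, this is an improvement that should be made. It is not a flaw in the trial's main comparison.

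**What to change.** Replace the two SAP sentences on the hematoma model with a rule that:
- states which hematoma grades form the outcome;
- includes the randomized arm in every fitted model, whatever its p value, and reports its adjusted odds ratio with a 95% interval;
- uses Firth penalized logistic regression with profile-likelihood p values and intervals, or at least LR p values, in place of Wald screening;
- limits covariates to a short prespecified list, its length tied to the number of events, containing only variables fixed before the envelope is opened;
- excludes any duration that ends at sheath removal (minor).

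The SAP is written in the past tense. If the model has already been fitted, the same specification can be run and labelled as a re-analysis.

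The cost is a few lines of SAP text and no new data. Firth estimates are slightly shrunk, one model term is reserved for the arm, and the fit may need a routine outside the named software. Keeping the arm and using Firth do not cure low power, so the interval for the arm may be wide. It should be reported as it is.
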